#### 6.1.2 Medical History and Demographic Information

The medical history comprises:

- General medical history
- Medication history
- Reproductive history.

The following demographic information will be recorded:

- Gender
- Age
- Ethnic origin
- Race
- Height
- Body weight
- Body mass index.

	Approved by: [name] [name]	Protocol No.: SARO.17.004.02.PROTOCOL Version No.: 2.0
---	------------------------------------	---

### 6.1.3 Clinical Laboratory Assessments

#### 6.1.3.1 Sample Collection

Blood samples will be collected for clinical laboratory testing at the time points indicated in the Schedule of Assessments (Table 1). Safety laboratory variables are listed in Table 4.

**Table 4 Safety Laboratory Assessments**

Hematology	Complete blood count, hemoglobin, PT, INR. Electrolytes (sodium, potassium, chloride and bicarbonate)
Clinical chemistry	LFT: ALT, AST, ALP, total bilirubin, GGT, total proteins and albumin. Amylase and lipase RFT: Serum creatinine, blood urea nitrogen, eGFR Cardiac marker: CK Lipid Panel and lipoprotein: TG, sdLDL, LDL, VLDL, HDL, total cholesterol, non HDL cholesterol, Apo A1 and Apo B Glycemic control: Fasting plasma glucose, HbA1c TSH
Urinalysis	Urine Chemical Examinations: pH, specific gravity, protein, glucose, bilirubin, urobilinogen, ketone bodies and nitrite Urine Microscopy: epithelial cells, RBCs, pus cells, cast and crystals
Serology	HIV type 1 and type 2 HAV IgM HBsAg HCV
Pregnancy test	Serum pregnancy test and urine pregnancy test for females of child-bearing potential

AST = aminotransferase; ALT = alanine aminotransferase; ALP = alkaline phosphatase; BUN = blood urea nitrogen; CK = creatinine kinase; eGFR = estimated Glomerular Filtration Rate; GGT =  $\gamma$ -glutamyl transferase; HAV IgM= anti hepatitis A virus; HbA1c = Glycosylated hemoglobin; HBsAg = hepatitis B surface antigen; HCV = hepatitis C virus; HDL = high-density lipoprotein; HIV = human immunodeficiency virus; INR = international normalized ratio; LDL = low-density lipoprotein; PT = Prothrombin time; sdLDL = Small dense low density lipoprotein; RBC = Red blood cell, sdLDL = Small dense low density lipoprotein; TSH = Thyroid stimulating hormone; VLDL = very low density lipoprotein.

#### 6.1.3.2 Urine Tests

Urine pregnancy test (females of child-bearing potential only at Visits 2, 3, 4, 5) will be processed by a local laboratory.

#### 6.1.3.3 Vital Signs

The following vital signs will be assessed at time points described in the Schedule of Assessments (Table 1):

- Sitting blood pressure (systolic and diastolic; mmHg)

	Approved by: [name] [name]	Protocol No.: SARO.17.004.02.PROTOCOL Version No.: 2.0
--	------------------------------------	---

 Zydus Discovery DMCC	CLINICAL TRIAL PROTOCOL Saroglitazar Magnesium – Phase 2 SARO.17.004	CONFIDENTIAL Page 43 of 76
--	---	---

- Pulse (beats per minute)
- Oral body temperature (°F)
- Respiratory rate (breaths per minute).

Vitals signs will be measured before any blood draw that occurs at the same visit and after the patient has been resting for at least 5 minutes.

#### **6.1.3.4 Twelve-lead Electrocardiograms**

Electrocardiograms will be performed locally at the study site in accordance with the Schedule of Assessments (Table 1). Subjects should be in resting position for 5 minutes before ECG recording and performed before any blood draw that occurs at the same visit.

#### **6.1.3.5 Physical Examinations**

Physical examinations will be performed in accordance with the Schedule of Assessments (Table 1). Patients' body weight will be recorded during all physical examinations. Height will be recorded at Screening Visit only).

### **6.2 EFFICACY**

#### **6.2.1 Primary Endpoint**

The primary endpoint is to assess the changes in NAFLD Activity Score (NAS) at week 24 from baseline and with no worsening of fibrosis in NASH patients.

[figure not shown]
#### **6.2.2 Secondary endpoints**

From baseline to Week 24:

1. To evaluate the percentage of responders in the treatment groups.

Responder is defined as a decrease from baseline of at least 2 points spread across at least 2 of the NAS components [steatosis, hepatocyte ballooning, and lobular inflammation] with no worsening of fibrosis.

2. Percentage of responders, defined by the disappearance of steatohepatitis.
3. Changes in the stage of steatosis, lobular inflammation and ballooning.
4. Changes in the stage of fibrosis.

	Approved by: [name] [name]	Protocol No.: SARO.17.004.02.PROTOCOL Version No.: 2.0
---	------------------------------------	---

 Zydus Discovery DMCC	CLINICAL TRIAL PROTOCOL Saroglitazar Magnesium – Phase 2 SARO.17.004	CONFIDENTIAL Page 44 of 76
--	---	---

5. Changes in the liver function tests.
6. Changes in the lipid profile.
7. Changes in the glycemic control and insulin resistance.
8. To assess the safety of Saroglitazar Magnesium 2 mg and 4 mg in patients with non-alcoholic steatohepatitis.

(Safety will be assessed during the study period through the reporting of AEs, by clinical laboratory tests, ECGs, vital sign, physical examination and body weight assessment at various time points during the study).

### 6.2.3 Blood Samples

Multiple venipunctures should be avoided to collect blood samples. It is recommended to collect blood sample for safety and efficacy measurement at a given visit.

Samples for secondary and exploratory efficacy variables will be assessed as follows:

[figure not shown]
- Liver function tests include ALT, AST, ALP, direct bilirubin, GGT, total proteins and albumin.
- Lipid parameters and lipoproteins include LDL, sdLDL, VLDL, HDL, triglyceride, total cholesterol, non HDL cholesterol, and Apolipoprotein A1, Apolipoprotein B.
- Glycemic control includes FPG, fasting insulin, adiponectin, C-peptide, HOMA IR, HOMA beta and HbA1c.

### 6.2.4 Total Amount of Blood

The total amount of blood drawn from each subject over the study will not exceed 500 mL.

## 6.3 APPROPRIATENESS OF MEASUREMENT

The endpoints chosen for the given study (safety and efficacy) are appropriate for the assessment of outcome of the study.

	Approved by: [name] [name]	Protocol No.: SARO.17.004.02.PROTOCOL Version No.: 2.0
---	------------------------------------	---

 Zydus Discovery DMCC	CLINICAL TRIAL PROTOCOL Saroglitazar Magnesium – Phase 2 SARO.17.004	CONFIDENTIAL Page 45 of 76
--	---	---

#### 6.4 ABNORMAL LABORATORY FINDINGS

In addition, a clinically significant value outside the normal or reference range in a routine safety assessment, such as clinical laboratory, vital signs or ECG, may signify an adverse finding. Additional examinations or repetition of test will be performed as medically indicated.

[figure not shown]
If the PI considers the abnormality as of medical relevance, he/she should also record this as an AE. If the findings contribute to a clinical diagnosis (e.g. hepatitis in case of increased liver enzymes), this diagnosis should be recorded as an AE.

The criteria for determining whether an abnormal objective test finding should be reported as an AE are as follows:

1. The test result is associated with accompanying symptoms, and/or
2. The test result requires additional diagnostic testing or medical/surgical intervention, and/or
3. The test result leads to change in study dosing or discontinuation from the study, significant additional concomitant drug treatment or other therapy, and/or
4. The test result leads to any of the outcomes included in the definition of an SAE, and/or
5. The test result is considered to be an AE by the PI or designee.

For any abnormal test result that meets one of the above conditions except for the last condition, the PI or designee will provide a justification in the source documentation for not reporting the abnormal test finding as an AE.

Each AE shall be evaluated for the severity, seriousness, duration, resolution, action taken and its association with the study drug. The study participant may be withdrawn or terminated from the study depending on the seriousness of the adverse event(s).

	Approved by: [name] [name]	Protocol No.: SARO.17.004.02.PROTOCOL Version No.: 2.0
---	------------------------------------	---

 Zydus Discovery DMCC	CLINICAL TRIAL PROTOCOL Saroglitazar Magnesium – Phase 2 SARO.17.004	CONFIDENTIAL Page 46 of 76
--	---	---

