## 9.4 PROCEDURES

### 9.4.1 Adverse Events

All AEs occurring during the course of the clinical study from the signing of the informed consent onwards will be collected, documented and reported to the Sponsor by the PI or designee according to the specific definitions and instructions detailed in this section. The Common Terminology Criteria for Adverse Event (CTCAE) (Version 4.03 or higher) system will be used for reporting and grading AEs.

An AE is defined as any untoward medical occurrence in a clinical investigation subject administered a pharmaceutical product and which does not necessarily have a causal relationship with this treatment.

Any medical condition already present at screening should not be reported as an adverse event unless the medical condition or signs or symptoms present at baseline changes in severity or seriousness at any time during the study. In this case, it should be reported as an adverse event.

Clinically significant abnormal laboratory or other examination (e.g. electrocardiogram) findings that are detected during the study or are present at screening and significantly worsen during the study should be reported as AEs. The PI will exercise his or her medical and scientific judgment in deciding whether an abnormal laboratory finding or other abnormal assessment is clinically significant. Clinically significant abnormal laboratory values occurring during the clinical study will be followed until repeat tests return to normal, stabilize, or are no longer clinically significant. Any abnormal test that is determined to be an error does not require reporting as an AE.

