7.3.2 Adverse Events

The applicable definition of an Adverse Event (AE) is in the study protocol section 9.4. A treatment-emergent AE (TEAE) is an event not present prior to exposure to study drug or any pre-existing event that worsens following exposure to study drug. The period for treatment-emergent AE analysis starts from the first exposure to the study drug until the patient exits the study. Adverse events (AEs) will be coded using MedDRA to give a preferred term and a SOC term for each event.

Descriptive summaries (frequencies and percentages) for specific TEAEs will be presented by system organ class and preferred term according to the Medical Dictionary for Regulatory Activities (MedDRA Version 19.1) dictionary. In addition to an overall presentation of all TEAEs, reports will be generated for special classes of TEAEs such as study drug related TEAEs, serious TEAEs, Maximum severity and TEAEs resulting in treatment discontinuation. These reports will be supported by individual patient listings, as necessary.

Adverse events will be counted by the number of events as well as the number of patients. For the summaries which count the number of patients, multiple TEAEs with the same MedDRA preferred term within the same subject will only be counted once.

Document Title:	Statistical Analysis Plan		
Version Number:	1.0	Date:	31 Mar 2020
Protocol Number:	SARO.17.004	Sponsor Name:	Zydus Discovery DMCC

Only patient listings will be provided for AEs that occur after signing informed consent but prior to exposure to investigational product. These listings will comprise all events occurring during this period in any subject who consented to participate in the study.

These listings will at least contain but not limited to information such as onset and resolution times, maximum severity, causal relationship to study treatment and action taken.

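### Protocol 6.4 lets a test result that changed dosing or had an SAE outcome stay out of the AE data on a source note, against 9.4.1; a laboratory-driven drug stop could then be missing from both the AE and disposition tables

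*Protocol*

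**What the plan says.** **Protocol 6.4.** Five conditions decide whether an abnormal objective test should be reported as an AE. Condition 3 opens with "The test result leads to change in study dosing or discontinuation from the study" and also covers significant added treatment. Condition 4 is "The test result leads to any of the outcomes included in the definition of an SAE". Condition 5 is that the investigator or designee already regards the result as an AE. The sentence after the list begins "For any abnormal test result that meets one of the above conditions except for the last condition" and continues that "the PI or designee will provide a justification in the source documentation for not reporting the abnormal test finding as an AE". It names no eCRF entry and no sponsor or medical review.

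The same section also says that an abnormality the investigator finds medically relevant should be recorded as an AE. Where findings contribute to a clinical diagnosis, "this diagnosis should be recorded as an AE".

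**Protocol 9.4.1.** For clinically significant abnormalities in laboratory or other examinations, "findings that are detected during the study or are present at screening and significantly worsen during the study should be reported as AEs". The only exemption it states for an abnormal test is one determined to be an error.

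**Protocol 9.4.2.** An SAE is defined as a kind of adverse event, and SAEs carry a 24-hour reporting duty.

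**SAP 7.3.2.** The special TEAE reports cover drug-related and serious events, "Maximum severity and TEAEs resulting in treatment discontinuation". All are built from AE records.

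**SAP section 5.** The disposition table counts patients who discontinued from the study, with the reason.

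**The concern.** The only condition that 6.4 keeps outside the source-note route is the one where the investigator has already called the result an AE. The two conditions with the most direct safety meaning, a change in dosing or discontinuation and an SAE outcome, are inside it. Under 9.4.1 the same result would ordinarily be an AE. Sites therefore have two rules for one result, and different sites may follow different ones.

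This matters because the liver criteria in Protocol 4.6 are triggered largely by ALT, AST, bilirubin and INR values, so drug stops that start from a laboratory result are foreseeable. A result not entered as an AE does not get the assessments of severity, seriousness, action taken and relation to study drug that 6.4 requires for every AE. It also does not count in any TEAE table. Safety is a stated secondary objective (Protocol 3.2).

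**Working it through.** The plan gives no figure to reproduce here; the check is a reading of the sections together, followed by simple arithmetic on size.

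**Step 1. Scope of the source-note sentence.** Five conditions less the last leaves conditions 1 to 4. Conditions 3 and 4 are inside by the plain wording. A stop or interruption of study drug is taken here to be a change in study dosing under condition 3.

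**Step 2. Comparison with 9.4.1.**
- 6.4: a result meeting conditions 1 to 4 may go unreported as an AE if a justification is in source. The acceptable grounds are not limited.
- 9.4.1: a clinically significant abnormal result should be reported; the one explicit exemption is a test error.

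A result that led to a dosing change or an SAE outcome is hard to describe as not clinically significant, so the two rules collide on exactly these cases.

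**Step 3. Follow one case through the outputs.** Take a patient whose study drug is stopped or interrupted for a laboratory result, with no diagnosis recorded, a justification in source and no AE record.
- *TEAE tables (SAP 7.3.2):* absent, including from the treatment-discontinuation report if the stop was permanent.
- *AE form (Protocol 4.5):* required only when the discontinuation is due to an AE.
- *Disposition (SAP section 5):* absent if the patient stays in the study. Protocol 4.6 provides for continued follow-up after a drug stop, so this is a planned situation.
- *Exposure (SAP 7.3.1):* an early permanent stop shortens treatment duration, which is summarised, but without a reason.
- *Laboratory outputs (SAP 7.3.4, Laboratory Results):* the values appear in the by-visit summaries and patient listings, and in the clinically significant listing if so judged. The shift table compares baseline with the last study visit, so a rise that has resolved by then need not show there. None of these outputs is planned to link a value to a drug stop.

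**Step 4. Size of one omission.** Inputs: arms of 6, 6 and 3 (Protocol 4.1 and 8.4; 15 × 2/5 = 6, 15 × 2/5 = 6, 15 × 1/5 = 3). Change in the observed rate = 1/n. Intervals are exact (Clopper-Pearson) 95%.

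| Group | n | Event omitted | Event recorded | Change |
|---|---|---|---|---|
| One active arm | 6 | 0/6 = 0% (0 to 45.9%) | 1/6 = 16.7% (0.4 to 64.1%) | 16.7 points |
| Placebo | 3 | 0/3 = 0% (0 to 70.8%) | 1/3 = 33.3% (0.8 to 90.6%) | 33.3 points |
| Both active arms | 12 | 0/12 = 0% (0 to 26.5%) | 1/12 = 8.3% (0.2 to 38.5%) | 8.3 points |

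The intervals overlap almost entirely, as they must at these sizes. The practical difference is between a table that shows no such event and one that shows one.

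**The case against.** The sentence in 6.4 can be read as an accountability rule: reporting is the default, and a departure must be justified in writing. Section 6.4 itself sends medically relevant abnormalities and resulting diagnoses to the AE form, and its own example is hepatitis from raised liver enzymes. An investigator who stops drug for a liver result has very probably judged it medically relevant. Monitors compare the eCRF with source (Protocol 9.2.2.1 and 9.2.5), so the note would be open to them. The size figures apply to any missing event in a trial this small.

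Much of this stands. It makes omission less likely and it limits what can be lost. It does not remove the conflict: the accountability reading still accepts non-reporting on grounds that 9.4.1 does not list, and monitoring is not given a rule for deciding which section governs.

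A reader might go further and infer that 6.4 excuses sites from SAE reporting, or hides these cases from the DMC. The documents do not support either inference. The sentence concerns the test finding and not the clinical event: a hospitalisation or a life-threatening event would ordinarily be an adverse event in its own right under 9.4.1 and 9.4.2, and the 24-hour duty expressly includes death from any cause. Protocol 7.4 has the DMC review safety data through periodic EDC reports, so laboratory values can reach it without an AE record.

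**Conclusion.** The point holds as a contradiction between Protocol 6.4 and 9.4.1 that leaves a limited gap in the safety tables. The gap is chiefly a laboratory-driven study-drug stop or interruption, in a patient who stays in follow-up, with no AE record. A patient who leaves the study is still counted in disposition with a reason.

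One omission would move the rate by 16.7 points in an active arm or 33.3 points in placebo. These figures are illustrative. They assume the planned arm sizes and a single event, and the documents give no basis for predicting how often the source-note route would be used. The texts show that such events can be missing, not that they will be. The conclusion also rests on 6.4 being applied as worded, and on no eCRF or data-management instruction outside these documents closing the gap.

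**What to change.** **Protocol 6.4.** State that a result leading to a dosing change or discontinuation (condition 3), or to an SAE outcome (condition 4), is recorded as an AE, and as an SAE where 9.4.2 applies, unless it is determined to be a test error. The error exemption is needed to agree with 9.4.1, since a dose may be interrupted on a result later found to be wrong. The source-note route can stay for conditions 1 and 2, and for the added-treatment part of condition 3, provided that clinically significant results still follow 9.4.1.

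**Data review.** Before database lock, reconcile every study-drug discontinuation and interruption against the AE dataset. Query each laboratory-driven one that has neither an AE record nor a documented test error.

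**Cost.** A few more AE records, one data-review check, and a protocol wording change to be handled under Protocol 9.5, where amendments need the protocol signatories and submission to the regulator and ethics committee. No stopping or dosing rule changes.

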## 7 INVESTIGATIONAL PLAN

### 7.1 STUDY DESIGN AND PLAN

This is a randomized, double-blind, placebo-controlled, study to evaluate safety and efficacy of Saroglitazar Magnesium 2 mg and 4 mg in patients with NASH. This study will be initiated after obtaining the approvals of Institutional Ethics Committee/Institutional Review Board (IEC/IRB) and the local Regulatory Authority.

It is the responsibility of the Principal Investigator (PI) to ensure that the study is conducted in accordance with the protocol, International Council for Harmonisation Good Clinical Practice, and all applicable regulatory requirements. Informed consent will be obtained before the start of any study related procedures.

[figure not shown]
As per the contemporary guidelines, the PI shall maintain Source Documents (SD), Site Master File (SMF), Informed Consent Forms/Documents (ICF/ICD) and other logs/forms during the conduct of a study.

All laboratory reports should be reviewed by the PI and/or his/her designee and any abnormal findings should be addressed. All protocol deviations occurring on the study shall be documented and the Sponsor and IEC/IRB informed.

Patients clinically suspected of NASH will be invited for a screening programme for inclusion in the study. Patients will be screened according to the inclusion and exclusion criteria. Clinical evaluation will be conducted for baseline characteristics and anthropometry measurements such as body weight and height.

After clinical evaluations, all baseline safety and efficacy parameters will be recorded as per Table 1. All laboratory collections will be performed following overnight fasting (at least 8 hrs).

Following confirmation of all clinical and laboratory inclusion and exclusion criteria, patients will continue into the screening period. During the screening period liver biopsy will be performed. However, if a biopsy was performed within 6 months the slides and biopsy material, or block, must be made available for baseline documentation. Such Patients, whose historical biopsy report is available, should not use medication suspected of having an effect on NASH from the 3 months prior to the screening.

	Approved by: [name] [name]	Protocol No.: SARO.17.004.02.PROTOCOL Version No.: 2.0
---	------------------------------------	---

 Zydus Discovery DMCC	CLINICAL TRIAL PROTOCOL Saroglitazar Magnesium – Phase 2 SARO.17.004	CONFIDENTIAL Page 47 of 76
--	---	---

If the patient has consumed restricted medications but is otherwise considered eligible to be enrolled into this study by the PI, a minimum of 1 month wash out period would be instituted before the screening visit.

Liver biopsy will be performed to confirm the diagnosis of NASH and record a baseline NAFLD Activity Score (Appendix 2). The histological evidence of NASH is defined as NAS  $\geq$  4 with a minimum score of 1 for all of its three components [steatosis, hepatocyte ballooning, and lobular inflammation].

Following confirmation of inclusion/exclusion criteria and upon histological confirmation of NASH by liver biopsy, patients will be enrolled into the study.

Eligible patients will be randomly assigned to receive Saroglitazar Magnesium 2 mg or 4 mg or placebo in a 2:2:1 ratio for 24 weeks.

Upon completion of 24 weeks of treatment, liver biopsy will be performed and the NAFLD Activity Score recorded (Appendix 2).

The scheduled visits during this study will be as follows:

- Visit 1: Screening Visit [-4 Week (-28 Days)],
- Visit 2: Enrollment Visit (Day 1  $\pm$  7 Days/Week 0),
- Visit 3: Day 43/Week 6  $\pm$  7 Days,
- Visit 4: Day 85/Week 12  $\pm$  7 Days,
- Visit 5: Day 127/Week 18  $\pm$  7 Days,
- Visit 6: Day 169/Week 24  $\pm$  7 Days,
- Visit 7: Follow-up Visit: Day 197/Week 28  $\pm$  7 Days,

Patients will be advised to follow a stable lifestyle. No change in the intensity of lifestyle (Diet/Exercise) will be allowed during the period of study. Patients will be monitored for safety and efficacy parameters as per Table No 1.

If further investigations are required in case of any AE, Investigator is advised to assess the AE and take necessary action, if required. Patients are advised to contact the Investigator for any complaints.

	Approved by: [name] [name]	Protocol No.: SARO.17.004.02.PROTOCOL Version No.: 2.0
---	---	---

 Zydus Discovery DMCC	CLINICAL TRIAL PROTOCOL Saroglitazar Magnesium – Phase 2 SARO.17.004	CONFIDENTIAL Page 48 of 76
---	---	---

[figure not shown]
